9.4 Biological Sample Retention and Destruction

The remainder of serum samples collected in accordance with Section 9.1.10, "Immunogenicity Evaluation" will be stored. Serum samples will be discarded after they will no longer be used. Details on sample retention will be provided in separately prepared handling procedures.

9.5 Amount and Frequency of Blood Collection

The total amount of blood to be collected from each subject will be as shown in [Table 9.a](#).

Table 9.a Amount and Frequency of Blood Collection

Test	Amount to be collected per collection	Frequency of collection	Total amount to be collected
Immunogenicity testing	20 mL	Three times	60 mL
Total amount to be collected			60 mL

10.0 ADVERSE EVENTS

10.1 Definitions

10.1.1 AEs

An AE is defined as any untoward medical occurrence in a clinical investigation subject who has signed informed consent to participate in a study; it does not necessarily have to have a causal relationship with this treatment or study participation.

An AE can therefore be any unfavorable and unintended sign (eg, a clinically significant abnormal laboratory finding), symptom, or disease temporally associated with the study participation whether or not it is considered related to the drug or study procedures.

10.1.2 Additional Points to Consider for AEs

An untoward finding generally may:

- Indicate a new diagnosis or unexpected worsening of a pre-existing condition. (Intermittent events for pre-existing conditions or underlying diseases should not be considered AEs.)
- Necessitate therapeutic intervention.
- Require an invasive diagnostic procedure.
- Require discontinuation or dose adjustment of the study drug or a concomitant medication.
- Be considered unfavorable by the investigator for any reason.

AEs caused by a study procedure (e.g., a bruise after blood draw) should be recorded as an AE.

Diagnoses vs signs and symptoms:

- Each event should be recorded to represent a single diagnosis. Accompanying signs (including abnormal laboratory values or ECG findings) or symptoms should NOT be recorded as additional AEs. However, each solicited local or systemic AE to be recorded in the subject diary should be recorded as a single event. If a diagnosis is unknown, sign(s) or symptom(s) should be recorded appropriately as an AE(s).

Pre-existing conditions:

- Pre-existing conditions (present since before the first vaccination with study drug) are considered present illnesses and should NOT be recorded as AEs. However, if the present illness worsens after the first vaccination with study drug, it should be appropriately recorded as an AE. The investigator should ensure that the AE term to be reported reflects a change from baseline (e.g., “worsening of...”).
- If a subject has a pre-existing episodic condition (eg, asthma, epilepsy) any occurrence of an episode should only be captured as an AE if the episodes become more frequent, serious or severe in nature, that is, investigators should ensure that the AE term recorded captures the change in the condition from Baseline (eg “worsening of...”).
- If a subject has a degenerative concurrent medical condition (eg, cataracts, rheumatoid arthritis), worsening of the condition should only be captured as an AE if occurring to a greater extent to that which would be expected. Again, investigators should ensure that the AE term recorded captures the change in the condition (eg, “worsening of...”).

Change in severity of AEs:

CONFIDENTIAL

- If the subject experiences a change in severity of an AE that is not related to starting the study drug or changing in the dose or regimen, the event should be captured once with the maximum severity recorded.

Preplanned surgeries or procedures:

- Preplanned procedures (surgeries or therapies) that are scheduled prior to signing of informed consent are not considered AEs. However, if a preplanned procedure is performed early (e.g., as an emergency) due to a worsening of the pre-existing condition, the worsening of the condition should be captured appropriately as an AE. Complications resulting from any planned surgery should be reported as AEs.

Elective surgeries or procedures:

- Elective procedures performed where there is no change in the subject's medical condition should not be recorded as AEs, but should be documented in the subject's source documents. Complications resulting from an elective surgery should be reported as AEs.

Insufficient clinical response (lack of efficacy):

- Insufficient clinical response, efficacy, or pharmacologic action, should NOT be recorded as an AE. The investigator must make the distinction between exacerbation of pre-existing illness and lack of therapeutic efficacy.

Overdose:

- The occurrence of overdose with no associated events should NOT be considered an AE, but instead will be documented on an Overdose page of the (e)CRF. Any event associated with overdose should be considered AEs and will be recorded on the AE page of the (e)CRF.

10.1.3 SAEs

An SAE is defined as any untoward medical occurrence in a clinical investigation subject administered a pharmaceutical product (including a study drug), which:

1. Results in DEATH.
2. Is LIFE THREATENING.
 - The term "life threatening" refers to an event in which the subject was at risk of death at the time of the event; it does not refer to an event that hypothetically might have caused death if it were more severe.
3. Requires inpatient HOSPITALIZATION or prolongation of existing hospitalization.
4. Results in persistent or significant DISABILITY/INCAPACITY.
5. Leads to a CONGENITAL ANOMALY/BIRTH DEFECT.
6. Is an IMPORTANT MEDICAL EVENT that satisfies any of the following:
 - May require intervention to prevent items 1 through 5 above.
 - May expose the subject to danger, even though the event is not immediately life threatening or fatal or does not result in hospitalization.
 - Includes any event or synonym described in the Takeda Medically Significant AE List ([Table 10.a](#)).

Table 10.a Takeda Medically Significant AE List

Term	
Acute respiratory failure/acute respiratory distress syndrome	Acute liver failure
Torsade de pointes / ventricular fibrillation / ventricular tachycardia	Anaphylactic shock
Malignant hypertension	Acute renal failure
Convulsive seizure (including seizure and epilepsy)	Pulmonary hypertension
Agranulocytosis	Pulmonary fibrosis (including interstitial lung disease)
Aplastic anemia	Confirmed or suspected endotoxin shock
Toxic epidermal necrolysis/Stevens-Johnson syndrome	Confirmed or suspected transmission of infectious agent by a medicinal product
Hepatic necrosis	Neuroleptic malignant syndrome / malignant hyperthermia
	Spontaneous abortion / stillbirth and fetal death

Note: The terms listed in this table may be “important medical events” that require the reporting of SAEs and are therefore broadly defined medical terms.

7. The following important medical events associated with the use of an influenza vaccine: neuritis, encephalitis, vasculitis, Guillain-Barre syndrome, Bell’s palsy (facial palsy), and demyelinating disorder (including acute disseminated encephalomyelitis [ADEM] and multiple sclerosis)

10.1.4 AEs of Special Interest

An AE of Special Interest (regardless of whether it is serious or not) is one of scientific and medical concern specific to the compound or program, for which ongoing monitoring and rapid communication by the investigator to Takeda may be appropriate. Such events may require further investigation in order to characterize and understand them.

10.1.5 Severity of AEs

The different categories of intensity are characterized as follows:

Mild: The event is transient and easily tolerated by the subject.
Moderate: The event causes the subject to interrupt the subject’s usual activities.
Severe: The event causes considerable interference with the subject’s usual activities.

However, pyrexia and injection site reactions (injection site pain, erythema, swelling, induration, and haemorrhage) should be assessed according to the classification specified in [9.1.11](#).

10.1.6 Causality of AEs

The relationship of each AE to study drug(s) will be assessed using the following categories:

Related: An AE that follows a reasonable temporal sequence from administration of a drug (including the course after withdrawal of the drug), or for which possible involvement of the drug cannot be ruled out, although factors other than the drug, such as underlying diseases, present illness, concomitant medications and concurrent treatments, may also be responsible.
Not related: An AE that does not follow a reasonable temporal sequence from administration of a drug and/or that can reasonably be explained by other factors, such as underlying diseases, present illness, concomitant medications and concurrent treatments.

CONFIDENTIAL

10.1.7 Relationship to Study Procedures

Relationship (causality) to study procedures should be determined for all AEs.

The relationship should be assessed as Related if the investigator considers that there is reasonable possibility that an event is due to a study procedure. Otherwise, the relationship should be assessed as Not Related.

10.1.8 Start Date

The start date of the AE is the date that the first signs/symptoms were noted by the subject and/or investigator.

The start date of AEs will be determined using the following criteria;

AEs	Start Date
Any signs/symptoms/diseases (diagnosis)	The date that the first signs/symptoms were noted by the subject and/or the investigator should be recorded.
Asymptomatic diseases	The date when examination was performed for diagnosis and diagnosis was confirmed should be recorded.
	The date when diagnosis was confirmed should also be recorded even when values or findings showed previous values or findings or the onset time can be estimated.
Worsening of present illnesses	The date when diagnosis was confirmed should also be recorded even when values or findings showed previous values or findings or the onset time can be estimated.

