Based on records from each subject's diary collected at Day 22 and 43 visits, the investigator will capture all AEs occurring during Days 1-22 and Days 22-43, and record these AEs on the (e)CRF together with the severity and causality assessment for each event.

As for pyrexia, the start date is defined as the date on which the first oral temperature measurement $\geq 38.0^{\circ}\text{C}$ is obtained, and the end date is defined as the date on which the first oral temperature measurement $<38.0^{\circ}\text{C}$ is obtained after the onset. Daily oral temperature measurements on Days 1-7 and Days 22-28 recorded in Diaries 1 and 3 should be transcribed to the (e)CRF even if they are $<38.0^{\circ}\text{C}$. If two or more temperature measurements are recorded for the same day, the highest temperature of that day should be transcribed to the (e)CRF.

The severity of pyrexia and injection site reactions will be assessed using the criteria shown below, by reference to the "FDA Guidance for Industry: Toxicity Grading Scale for Healthy Adult and Adolescent Volunteers Enrolled in Preventive Vaccine Clinical Trials" [7]. For other AEs (including solicited systemic reactions to be recorded in the subject diary), assessment will be performed as specified in Section 10.1.5.

Pyrexia:

Mild: $\geq 38.0^{\circ}\text{C}$ and $<38.5^{\circ}\text{C}$

Moderate: $\geq 38.5^{\circ}\text{C}$ and $<39.0^{\circ}\text{C}$

Severe: $\geq 39.0^{\circ}\text{C}$

Measurable injection site reactions (injection site erythema, swelling, and induration):

Mild: ≥ 2.5 cm and <5.1 cm

Moderate: ≥ 5.1 cm and <10.1 cm

Severe: ≥ 10.1 cm

*Injection site reactions <2.5 cm will not be regarded as AEs. However, the longest diameter recorded in the diary will be transcribed to the (e)CRF separately from AEs, regardless of whether it is ≥ 2.5 cm or <2.5 cm.

Injection site pain and haemorrhage:

Mild: No interference with upper extremity movement

Moderate: Interference with upper extremity movement present.

Severe: Upper extremity impairment/dysfunction

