10.1.8 Start Date

The start date of the AE is the date that the first signs/symptoms were noted by the subject and/or investigator.

The start date of AEs will be determined using the following criteria;

AEs	Start Date
Any signs/symptoms/diseases (diagnosis)	The date that the first signs/symptoms were noted by the subject and/or the investigator should be recorded.
Asymptomatic diseases	The date when examination was performed for diagnosis and diagnosis was confirmed should be recorded.
Worsening of present illnesses	The date when diagnosis was confirmed should also be recorded even when values or findings showed previous values or findings or the onset time can be estimated.

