10.2.1.2 AE Reporting

At each study visit, the investigator will assess whether any subjective AEs have occurred. A neutral question, such as “How have you been feeling since your last visit?” may be asked. Subjects may report AEs occurring at any other time during the study.

All subjects experiencing AEs after the first exposure to study drug, whether considered associated with the use of the study drug or not, must be monitored until the symptoms subside and any clinically relevant changes in laboratory values have returned to baseline or until there is a satisfactory explanation for the changes observed. All AEs will be documented in the AE page of the (e)CRF, whether or not the investigator concludes that the event is related to the drug treatment. The following information will be documented for each event:

1. Event term
2. Start and end date
3. Pattern
4. Severity
5. Investigator’s opinion of the causality between the event and administration of study drug(s)
6. Investigator’s opinion of the causality to study procedure(s), including the details of the suspected procedure

CONFIDENTIAL

7. Action taken with study treatment
8. Outcome of event
9. Seriousness
10. Treatment emergent (After the first exposure to study drug)
11. For pyrexia, the maximum body temperature and the presence or absence of a 24-hour or longer persistence
12. For injection site erythema, swelling, and induration, the longest diameter

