7.1.2 Definition of Study Days

- Study Day of the initial vaccination: The day before the initial vaccination will be Day -1, while the day of the initial vaccination will be Day 1.
- Study Day of the second vaccination: The day of the second vaccination will be Day 1.

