7.11.1.2 Displays of Treatment-Emergent Adverse events

Analysis set: Safety analysis set

Analysis variable(s): TEAE

Categories: Intensity [Mild, Moderate, Severe]
Vaccination number [Initial vaccination, Second vaccination]
Timing of onset by vaccination number [Day 1 of the initial vaccination \leq - \leq Day 7 of the initial vaccination, Day 8 of the initial vaccination \leq - \leq Before the second vaccination]
[Day 1 of the second vaccination \leq - \leq Day 7 of the second vaccination, Day 8 of the second vaccination \leq - \leq Max]

Analysis methods: The following summaries will be provided for the above analysis variables using frequency tabulations.

TEAEs will be coded using the MedDRA and summarized by SOC and PT. SOC will be sorted alphabetically and PT in decreasing frequency for tables provided by SOC and PT. SOC and PT will be sorted in decreasing frequency for tables provided by SOC only or PT only.

- (1) TEAEs by SOC and PT
- (2) TEAEs by SOC
- (3) TEAEs by PT
- (4) Drug-related TEAEs by SOC and PT
- (5) Intensity of TEAEs by SOC and PT
- (6) Intensity of drug-related TEAEs by SOC and PT
- (7) TEAEs leading to study drug discontinuation by SOC and PT
- (8) Serious TEAEs by SOC and PT

(9) Vaccination number of TEAEs by SOC and PT
(10) Vaccination number and timing of onset of TEAEs by SOC and PT

For each frequency tabulation, the number and percentage of subjects will be obtained according to the rules below.

[Number of subjects]

- Summaries other than (5), (6), (9), and (10)
A subject with multiple occurrences of TEAE within a SOC will be counted only once in that SOC. A subject with multiple occurrences of TEAE within a PT will be counted only once in that PT. The percentage of subjects with TEAEs will be calculated using the number of subjects in the safety analysis set as the denominator.
- Summaries for (5) and (6)
A subject with multiple occurrences of TEAE within a SOC or a PT will be counted only once for the TEAE with maximum intensity in that SOC or PT. The percentage of subjects with TEAEs will be calculated using the number of subjects in the safety analysis set as the denominator.
- Summary for (9)

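### The start-date rule for worsening of a present illness conflicts with the section's own definition and can put an early-onset event in the wrong onset interval of the TEAE tables

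*Protocol*

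**What the plan says.** Protocol 10.1.8 begins with a general rule: "The start date of the AE is the date that the first signs/symptoms were noted by the subject and/or investigator". A table of criteria by type of event follows. For signs, symptoms and diagnosed diseases in general, the Start Date column repeats the rule: "The date that the first signs/symptoms were noted by the subject and/or the investigator should be recorded". For worsening of present illnesses it says something different, and applies it even to an onset that is open to estimation: "The date when diagnosis was confirmed should also be recorded even when values or findings showed previous values or findings or the onset time". That row contains no first-noted date. The protocol file holds two protocol versions, and both carry this wording in the worsening row.

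These events are within scope. Under 10.1.2, "if the present illness worsens after the first vaccination with study drug, it should be appropriately recorded as an AE". The data listed for each AE in 10.2.1.2 include "Start and end date", with no diagnosis date and no clock time of onset.

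SAP 7.11.1.2 tabulates TEAEs by vaccination number and by "Timing of onset by vaccination number". For the initial vaccination the intervals are Days 1 to 7, and Day 8 until before the second vaccination. For the second they are Days 1 to 7, and Day 8 onward. SAP 7.1.2 sets the clock: "Study Day of the second vaccination: The day of the second vaccination will be Day 1". SAP 7.1.5 gives no convention for missing AE dates. The SAP does not say how an AE dated on the day of dose 2 is assigned to a dose.

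**The concern.** For a symptomatic worsening whose onset is known or can be estimated, the opening sentence and the table row give different dates, and only one start-date entry is listed. After Day 1 the scheduled visits are Visit 2, which is the day of dose 2, and Visit 3. The investigator reviews the diaries at those visits, so confirmation at a visit is a foreseeable path. A worsening noted on Day 3 and confirmed at Visit 2 could then be dated Day 22. One noted two days after dose 2 and confirmed at Visit 3 could be dated Day 43.

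What is at stake is whether the TEAE tables by dose and onset interval place such events correctly in time. Those tables are where a reader looks for a cluster of events in the week after a dose.

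**Working it through.** The plan has no figure to reproduce: the sample size of 55 is stated to have no statistical rationale, and the point concerns a dating rule. The check is to take each possible onset day, replace it by the date of the visit at which the event is confirmed, and compare the SAP 7.11.1.2 cell (dose and onset interval) before and after.

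**Inputs**
- Visit 2 on Day 22, allowed 0 to 2 days late (Protocol Appendix A).
- Visit 3 at Visit 2 + 21 days, allowed +19 to +23 (Appendix A).
- Intervals split between Day 7 and Day 8 after each dose (SAP 7.11.1.2).
- Study Day of dose 2 = calendar day - Visit 2 day + 1 (SAP 7.1.2). With Visit 2 on Day 22, Day 28 is 28 - 22 + 1 = 7 and Day 43 is 43 - 22 + 1 = 22.
- Assumption: confirmation happens at a scheduled visit and its date is entered as the start date.

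**Results with Visit 2 on Day 22 and Visit 3 on Day 43**

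| Case | True onset | Dated to | Dose wrong | Cell wrong |
|---|---|---|---|---|
| A | Days 1-21 | Visit 2, treated as before dose 2 | 0 of 21 | 7 of 21 |
| B | Days 1-21 | Visit 2, assigned by calendar date alone | 21 of 21 | 21 of 21 |
| C | Days 22-42 | Visit 3 | 0 of 21 | 7 of 21 |
| D | Days 1-21 | Visit 3 (first confirmed after dose 2) | 21 of 21 | 21 of 21 |

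In A the 7 wrong days are onsets on Days 1-7, moved to the interval from Day 8. The other 21 - 7 = 14 onset days do not change cell. In C the 7 are onsets on Days 22-28, which are Days 1-7 of dose 2, and again 14 days do not change.

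**Visit windows.** With Visit 2 on Day 23 or 24, A still gives 7 wrong days, now out of 22 or 23; B and D become 22 of 22 or 23 of 23. Moving Visit 3 within its window changes the number of onset days in C to between 19 and 23, but the 7 remain. The largest date error up to the next visit is 24 - 1 = 23 days (onset on Day 1, Visit 2 on Day 24).

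**If the first-noted date is used,** no event changes cell.

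**Size per subject.** With 55 subjects receiving both doses, one misplaced subject takes 1/55 = 1.8 percentage points from one cell and adds them to another. Two give 2/55 = 3.6 and three give 3/55 = 5.5. The counts in the table are onset days, not probabilities: the documents say nothing about how onsets are distributed.

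**The case against.** **The word *also*.** The row says the confirmation date should also be recorded, which can mean in addition to the onset date. A reader might infer that the row overrides a date the subject wrote in the diary; the text does not say so. This stands as an ambiguity, but it does not clear the row. The row gives no other date, it sits under the Start Date heading, and 10.2.1.2 lists nowhere to put a second date.

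**A table artefact.** In the earlier protocol version in the file, the same sentence also appears beneath the asymptomatic-disease entry, so a merged cell may have been split when the PDF was read. Which other rows it governs cannot be settled. Both versions nevertheless place it in the worsening row.

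**The dose column.** A reader might infer that any dose 1 event confirmed at Visit 2 is counted against dose 2. The SAP does not support that as a general result. Its dose 1 interval runs until before the second vaccination, not to a calendar day. Appendix A has Diaries 1 and 2 collected before vaccination at Visit 2, and Protocol 9.3.3 lists AE collection ahead of the vaccination. Handled that way, case A applies and no dose is wrong. Cases B and D need further conditions.

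**Confirmation at a visit.** Subjects may report AEs at any time (10.2.1.2) and may attend another institution between visits (7.4), so confirmation need not wait. This stands: the misplacement is conditional.

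**Scope.** A reader might extend the problem to reactogenicity generally. The row covers only illnesses present before the first dose. New symptoms use the first-noted date, and 10.1.2 has each solicited reaction recorded as its own event. Pyrexia has its own rule in 9.1.11: "As for pyrexia, the start date is defined as the date on which the first oral temperature measurement" reaches 38.0 °C. Nor are the AE tables the only results split by dose: reaction diameters (SAP 7.11.5.1) and vital signs (SAP 7.11.3) are too.

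**Conclusion.** The conflict is real and its effect is small. Protocol 10.1.8 defines the start date one way and, for worsening of a present illness, tabulates another. If a site follows the row and confirmation waits for the next scheduled visit, onsets on Days 1-7 after either dose fall in the wrong interval of SAP 7.11.1.2 (7 of 21 onset days). The dose is wrong only if an AE dated on the day of dose 2 is assigned by calendar date alone, or if a dose 1 event is first confirmed after dose 2.

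Few events are likely to be affected. Subjects are healthy adults aged 20 to 49. Exclusion criterion 6 removes poorly controlled, clinically significant disorders that may affect participation or confound results, although stable illnesses can enter. The documents give no expected number of worsenings. Assuming 0 to 3 affected subjects, the shift in a cell is 0 to 5.5 percentage points. The tables are descriptive. Overall TEAE counts, pyrexia and every immunogenicity endpoint are unaffected. This is a worthwhile clarification, not a threat to the study's conclusions.

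**What to change.** In the 10.1.8 row for worsening of present illnesses, make the start date the date the worsened sign or symptom was first noted, using the diary date where there is one. Keep the confirmation date as the start date only for a worsening without symptoms. If the diagnosis date is wanted as well, hold it in a separate field.

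In SAP 7.11.1.2, add one line: AEs dated on the day of the second vaccination but noted before it are assigned to the initial vaccination. For diary-recorded events the order can be read from the diary used, since Diary 2 ends before the Day 22 visit and Diary 3 starts after vaccination that day.

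The cost is one table row, the matching eCRF completion guidance and one SAP sentence. No new visit or procedure is needed. If the eCRF cannot show whether an AE dated on the day of dose 2 came before or after the injection, a single tick box for those events would do it.
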